#### 5.1.3.1 Primary Effectiveness Endpoint

The primary effectiveness analysis based on UCP is summarized in the following table. Subjects with baseline LFS score as assessed by EI of Minimal, Mild, or Moderate are enrolled in the study. A LFS (as assessed by EI) responder is defined as a subject with at least one grade improvement from baseline on 5-point LFS as assessed by EI.

**Table 5-15 Primary Effectiveness Analyses**

Endpoint	Description	Timing	Methodology
LFS Responder as assessed by EI	Superiority of VOLBELLA with Lidocaine over no-treatment control  Number (%) of responders by treatment group (mITT population)	Month 3	Responder exact test

The primary effectiveness analysis will be performed based on the mITT population without any missing data imputation. For treatment subjects, assessments within window will be used. For control subjects who do not receive optional treatment, the assessments within month 3 window will be used. For control subjects who receive optional treatment, the assessments within month 3 window and before optional treatment will be used. Sensitivity analysis will be performed using missing data handling conventions as described in Section 5.1.1.4 as well as using PP population.

### 5.1.3.2 Secondary Effectiveness Endpoints

The secondary effectiveness analysis based on UCP is summarized in the following table.

**Table 5-16 Secondary Effectiveness Analyses**

Endpoint	Description	Timing	Methodology
LFS responder as assessed by subject	Number (%) of responders by treatment group	Month 3	Responder exact test within group (treatment group only)
Change from baseline in overall lip volume	Summary by treatment group	Month 3	CFB 2-sample t-test or Wilcoxon test
Percentage change from baseline in lip surface area	Summary by treatment group	Month 3	CFB 2-sample t-test or Wilcoxon test

[REDACTED]

[REDACTED]

[REDACTED]

[REDACTED]

[REDACTED]

[REDACTED]

[REDACTED]

[REDACTED]

[REDACTED]

[REDACTED]

[REDACTED]

[REDACTED]

[REDACTED]

[REDACTED]

[REDACTED]

[REDACTED]

[REDACTED]

[REDACTED]

[REDACTED]

[REDACTED]	[REDACTED]	[REDACTED]	[REDACTED]
[REDACTED]	[REDACTED]	[REDACTED]	[REDACTED]
[REDACTED]	[REDACTED]	[REDACTED]	[REDACTED]
[REDACTED]	[REDACTED]	[REDACTED]	[REDACTED]
[REDACTED]	[REDACTED]	[REDACTED]	[REDACTED]
[REDACTED]	[REDACTED]	[REDACTED]	[REDACTED]
[REDACTED]	[REDACTED]	[REDACTED]	[REDACTED]
[REDACTED]	[REDACTED]	[REDACTED]	[REDACTED]
[REDACTED]	[REDACTED]	[REDACTED]	[REDACTED]
[REDACTED]	[REDACTED]	[REDACTED]	[REDACTED]
[REDACTED]	[REDACTED]	[REDACTED]	[REDACTED]
[REDACTED]	[REDACTED]	[REDACTED]	[REDACTED]
[REDACTED]	[REDACTED]	[REDACTED]	[REDACTED]
[REDACTED]	[REDACTED]	[REDACTED]	[REDACTED]
[REDACTED]	[REDACTED]	[REDACTED]	[REDACTED]
[REDACTED]	[REDACTED]	[REDACTED]	[REDACTED]
[REDACTED]	[REDACTED]	[REDACTED]	[REDACTED]
[REDACTED]	[REDACTED]	[REDACTED]	[REDACTED]
[REDACTED]	[REDACTED]	[REDACTED]	[REDACTED]
[REDACTED]	[REDACTED]	[REDACTED]	[REDACTED]
[REDACTED]	[REDACTED]	[REDACTED]	[REDACTED]
[REDACTED]	[REDACTED]	[REDACTED]	[REDACTED]

### 5.1.4 Safety Analyses

Safety analyses will be based on the Safety Population.

#### 5.1.4.1 Study Treatment Exposure and Compliance

See Sections 5.1.2.8 and 5.1.2.9

#### 5.1.4.2 Adverse Events

The following treatment emergent adverse event (TEAE) terms are defined:

**Table 5-18 AE Terms**

Term	Description	Timing
Treatment group	An event that initially occurs or increases in severity on or after the treatment and before safety day 91 (month 3) (For treatment group, TEAEs during UCP consist a subset of TEAEs during TP.)	UCP
	An event that initially occurs or increases in severity on or after the treatment	TP
Control Group	An event that initially occurs or increases in severity on or after randomization and before optional treatment at month 3	UCP
	An event that initially occurs or increases in severity on or after optional treatment at month 3	TP

AEs, encompassing abnormalities reported as occurring after the Screening Visit, will be coded using MedDRA version 18.1 or newer. A listing for all AEs in the treatment and control groups will be presented. Additionally, unique subjects reporting AEs as well as number of events in the following AE categories will be summarized for treatment subjects, control subjects after treatment, and all treated subjects as listed in Table 5-19. AEs during UCP will be listed only.

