8.1 Analysis Populations

The following analysis populations will be used in the analyses for this study:

- modified intent-to-treat (mITT) population: subjects who are randomized to study treatment (treatment group) and receive at least 1 study device treatment and have baseline and at least 1 posttreatment assessment of the primary variable, and subjects who are randomized to the no-treatment control group and have baseline and at least 1 follow-up assessment of the primary variable
- per-protocol (PP) population: all mITT subjects who do not have any significant protocol deviations affecting the primary effectiveness endpoint
- safety population: subjects who receive at least 1 study treatment

Unless specified otherwise, effectiveness analyses will be conducted using the mITT population. The PP population will be used to perform sensitivity analyses for the primary effectiveness variable. All safety analyses will be conducted using the safety population.

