**Table 5-1 Analysis Populations**

Population	Definition	Study Treatment
Modified Intent-to-Treat (mITT) population	
 
All subjects who are randomized to study treatment (treatment group) and receive at least 1 study device treatment and have baseline and at least 1 post-treatment assessment of the primary variable
 
All subjects who are randomized to the no-treatment control group and have baseline and at least 1 follow-up assessment of the primary variable
 
	As treated
Per-protocol (PP) population	All mITT subjects who have baseline LFS score of Minimal, Mild, or Moderate, have Month 3 LFS assessments, and do not have any significant protocol deviations affecting the primary effectiveness endpoint	As treated
Safety population	
 
All subjects randomized to the treatment (treatment group) who receive at least 1 study treatment
 
All subjects randomized to the control group
 
	As treated

Subjects will be analyzed as treated. All effectiveness analyses will be performed using the mITT population. Additional sensitivity analyses for the primary effectiveness analysis will also be performed using PP population. All safety analyses will be performed using the safety population.

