
Analysis day                      Safety Day
	
VOLBELLA Group                      Relative to the immediate prior treatment date (initial or touch-up)
 
If analysis date <math>\geq</math> initial treatment date:
 
 
• Safety Day = analysis date – immediate prior treatment date + 1
 
• Safety Day 1 = immediate prior treatment date
 
 
If analysis date <math><</math> initial treatment date:
 
 
• Safety Day = analysis date – immediate prior treatment date
 
• Safety Day -1 = day before immediate prior treatment date
 
 
Control group before receiving treatment                      Relative to the randomization date
 
If analysis date <math>\geq</math> randomization date:
 
 
• Safety Day = analysis date –randomization date +1
 
• Safety Day 1 = randomization date
 
 
If analysis date <math><</math> randomization date:
 
 
• Safety Day = analysis date –randomization date
 
• Safety Day -1 = day before randomization date
 
 
Treated Control after receiving treatment                      Relative to the immediate prior treatment date (initial or touch-up)
 
If analysis date <math>\geq</math> initial treatment date:
 
 
• Safety Day = analysis date – immediate prior treatment date + 1
 
• Safety Day 1 = immediate prior treatment date
 

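### No by-arm adverse-event summary is planned for the untreated control period, so the randomised background rate is collected but never tabulated

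*SAP*

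**What the plan says.** SAP 5.1 divides the study into the UCP (up to Month 3) and the treated period (TP). SAP Table 5-18 defines treatment-emergent events for each arm in each period. For the treatment group, UCP events are those starting or worsening "on or after the treatment and before safety day 91 (month 3"). For controls, the definition is "An event that initially occurs or increases in severity on or after randomization and before optional treatment at month 3".

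The text under that table says summaries "will be summarized for treatment subjects, control subjects after treatment, and all treated subjects as listed in Table 5-19", and then: "AEs during UCP will be listed only". Every row of Table 5-19 is timed TP, and no column is planned for untreated controls.

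Protocol 8.3.4 has the same rule. Events before treatment are listed and not summarised, and it names the controls' time before optional treatment as part of this.

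The safety populations differ. Protocol 8.1 has "safety population: subjects who receive at least 1 study treatment". SAP Table 5-1 keeps the treated-subject condition for the treatment group but adds "All subjects randomized to the control group". SAP 5.3.2, which records changes to the analyses, mentions only a dropped cross table.

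**The concern.** The design keeps about a quarter of subjects untreated for three months and collects adverse events from consent onwards (Protocol 11.1.1 and 11.2). That gives a randomised estimate of how often events occur without the device. Under the current plan a reader sees event rates after injection but no rate from the untreated arm to set beside them.

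Without that rate, attribution rests mainly on the relatedness judgement. Protocol 11.1.8 gives this to the Treating Investigator alone, and Protocol 4.3.3 states that the Treating Investigator is not blinded. A background rate would be a simple check on it. The SAP has already defined the control-arm UCP events and brought untreated controls into the safety set, yet neither step leads to an adverse-event summary.

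**Working it through.** **Stated figures.** Neither document gives a power or precision for any adverse-event comparison. The only sample-size claim is power above 96% for the primary endpoint (Protocol 8.5). Exact enumeration of the two-sided Fisher test with 111 against 37 subjects and 79.0% against 44.1% gives 96.7%, so that claim reproduces. It does not bear on safety.

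**What is summarised** (SAP Tables 5-18 and 5-19 and the text between them)

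| Events | Defined | Listed | Summarised |
|---|---|---|---|
| Treatment arm, UCP | yes | yes | only within TP totals (a subset of TP) |
| Controls, UCP | yes | yes | no |
| Controls after treatment, TP | yes | yes | yes |

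Planned by-arm UCP adverse-event summaries: 0.

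**Length of the UCP**
- Safety Day in the treatment arm is "Relative to the immediate prior treatment date (initial or touch-up") (SAP Table 6-1), with Day 1 the treatment date. The optional touch-up is at the day 30 visit after initial treatment.
- No touch-up: Safety Days 1 to 90, which is 90 days.
- Touch-up 30 days later: the count restarts, giving 30 + 90 = 120 days from first injection, and 120 / 90 = 1.33.
- Mean length at assumed touch-up rates of 0%, 50% and 100%: 90 + 30 × rate = 90, 105 and 120 days.
- Controls: from randomization to optional treatment. This is about 90 days if treatment is given at month 3, but Table 5-18 sets no day limit and no end for a control who declines.

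**Precision of a by-arm table.** The documents give no adverse-event rates, so those below are assumptions. With 132 and 44 randomised (Protocol 5.1) and the same rate p in both arms, the 95% half-width is 1.96 × √[p(1 − p)(1/132 + 1/44)], where 1/132 + 1/44 = 0.0303.
- p = 10%: 1.96 × √(0.09 × 0.0303) = 10.2 points
- p = 20%: 1.96 × √(0.16 × 0.0303) = 13.6 points
- p = 30%: 1.96 × √(0.21 × 0.0303) = 15.6 points

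If only the 111 and 37 expected at month 3 contributed, 1/111 + 1/37 = 0.0360, and the same formula gives 11.2, 14.9 and 17.1 points.

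With unequal rates at 132 and 44, the half-width is 1.96 × √[p₁(1 − p₁)/132 + p₀(1 − p₀)/44]. This gives 9.4 points for 20% treated against 5% untreated, and 11.8 points for 30% against 10%. If no control had an event, the one-sided 95% upper bound on the background rate would be 1 − 0.05^(1/44) = 6.6%. Such a table is imprecise but informative.

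**The case against.** The strongest defence is that the rule was pre-specified. Protocol 8.3.4 lists the controls' pre-treatment events without summarising them, and the SAP carries that out. The safety objective in SAP Table 4-1 is to evaluate, with no stated intent to compare. Both points stand. The by-arm table is an addition to the protocol's plan and should be recorded as one. They do not supply the missing background rate.

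Ascertainment also differs. Treated subjects have a 30-day diary and a day-3 telephone call after each treatment, while controls attend at months 1 and 3 (Protocol synopsis). More contact may produce more reports, and a common window does not remove that. This stands as a limit on interpretation.

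A reader might infer more than the documents support:
- *That no controlled safety data are summarised at all.* SAP Table 5-22 summarises vital signs at UCP Months 1 and 3. The gap concerns adverse events.
- *That the unequal windows or safety sets cause the gap or distort a planned result.* The listing rule alone removes the comparison. UCP events feed only listings, so the window changes no planned adverse-event statistic. Its net direction is also open, because the control period has no day limit.
- *That controls who declined treatment dilute the treated-period rates.* The text under Table 5-18 limits the summaries to treated groups, and SAP 5.1.2.8 likewise refers to treated controls. The denominator is worth stating, but no error follows from the text.
- *That device effects cannot be separated from background events.* Relatedness, the split by injection site in Table 5-19 and the injection-site diaries all help. They are imperfect, and the first is unblinded.

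**Conclusion.** The point holds for adverse events. The trial's only randomised adverse-event comparison is not planned, and the untreated controls' background rate is never summarised, although the data are collected and the events are already defined. The plan agrees with Protocol 8.3.4, so this is a gap in a deliberate choice and not a conflict between the documents on that rule. The primary analysis and every planned summary are unaffected.

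A by-arm table would give a difference to within about 10 to 16 points at assumed rates of 10% to 30% with 132 and 44 subjects. It would be open-label, imprecise and subject to closer ascertainment in the treated arm, so it should be read descriptively. The window figure (about 120 days against 90) assumes a touch-up 30 days after first injection. It matters only if the comparison is made.

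Separately, the SAP safety population differs from the one in Protocol 8.1, and SAP 5.3.2 does not record this.

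**What to change.** 1. Add a descriptive UCP block to SAP Table 5-19: subjects with any adverse event, any serious adverse event, and events by system organ class and preferred term, as n and % by randomised arm. Give the 95% confidence interval for the difference in any adverse event.
2. Use one window for this block: Days 1 to 90 from initial treatment (treatment arm) or from randomization (controls), censored at optional treatment. After a touch-up on day 30 this leaves about 90 − 30 = 60 days of post-touch-up follow-up in the block; later events still appear in the TP tables.
3. Use the SAP safety set for the UCP block, and state that treated subjects are the denominator for all TP tables.
4. Record in SAP 5.3.2 that the block is an addition to Protocol 8.3.4, and that the SAP safety population differs from Protocol 8.1.
5. Footnote the table: open-label reporting, limited precision, and diaries and day-3 calls in treated subjects only.

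The cost is one descriptive table from data already collected and a few sentences in the SAP. It needs no hypothesis test and uses no alpha.

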**Table 5-19 AE Summaries**

Endpoint	Description	Timing	Methodology
Overall summary	Treatment-emergent AEs (TEAEs) 
 
• Treatment-related TEAEs               
 
○ At injection site
 
○ Not at injection site
 
 
 
• All Serious AEs (SAEs)               
 
○ Treatment-related SAE                   
 
▪ At injection site
 
▪ Not at injection site
 
 
 
 
 
• Discontinued due to TEAE
 
• Deaths
 
	TP	Categorical counts, Event descriptives
TEAEs	
 
• Overall summary and by SOC, PT, and severity
 
	TP	Categorical counts, Event descriptives
Treatment-related	
 
• Overall summary and by SOC, PT, and severity
 
	TP	Categorical counts,

Endpoint	Description	Timing	Methodology
TEAEs	severity 
 
Overall summary by duration, time to onset, outcome, and treatment required
 
		Event descriptives
SAEs	Overall summary and by PT	TP	Listing
AEs leading to discontinuation	Overall summary and by PT	TP	Listing

Note: SOCs will be sorted alphabetically; PTs will be sorted in descending frequency in the treatment group. AEs for control group after optional treatment are summarized.

Time to onset for TEAEs will be computed as

$$\text{AE start date} - \text{reference date} + 1,$$

where the reference date is initial treatment date for TEAEs occurring on or after initial treatment but before touch-up treatment, and the reference date is touch-up treatment date for TEAEs occurring on or after touch-up treatment.

Duration for TEAEs will be computed as AE end date – AE start date + 1.

### 5.1.4.3 Injection Site Responses (ISR)

ISRs recorded in subject diaries after each treatment (initial, touch-up) will be summarized for that treatment by predefined symptoms.

**Table 5-20**                      **ISR Analyses**

Endpoint	Description	Timing	Methodology
ISR severity	Maximum reported severity	Initial, Touch-up	Categorical counts
ISR duration	Duration from first instance of the symptom to the last instance of the symptom within the treatment period, where last instance means no further symptoms till the end of the 30-day diary period. Duration is derived as date of last ISR minus date of first ISR plus one.	Initial, Touch-up	Categorical counts
ISR	All ISR Diary analysis day will be derived using diary date minus last treatment date plus one.	Initial, Touch-up	Listing

### 5.1.4.4 Procedural Pain

Subject assessment of procedural pain (pain during injection) on an 11-point scale ranging from 0 (no pain) to 10 (worst pain imaginable) after initial treatment will be summarized.

**Table 5-21**                      **Procedural Pain Analyses**

Endpoint	Description	Timing	Methodology
----------	-------------	--------	-------------

Endpoint	Description	Timing	Methodology
Procedural pain	Summary of pain scores as continuous scale	Initial	Continuous descriptive

### 5.1.4.5 Clinical Laboratory Assessments

Clinical laboratory assessments are taken at Screening, Month 1 and Month 6. Subjects with at least one abnormal finding will be listed for the Safety Population.

### 5.1.4.6 Vital Signs and Physical Measurement

Vital signs and physical measurement (height and weight) will be listed and summarized for the Safety Population.

**Table 5-22 Physical Examination Analyses**

Endpoint	Description	Timing	Methodology
Vital signs	Summary of blood pressure (systolic and diastolic in a sitting position), temperature, pulse, and respiratory rates	Month 1, 3 (UCP), Month 1, 3, 6 (TP)	Continuous descriptives
Physical measurement	Summary of height, weight, and BMI	Screening	Continuous descriptives

### 5.1.4.7 Electrocardiograms

Electrocardiograms (EKG) will be taken at Screening and initial treatment visit. Subjects with abnormal finding will be listed.

### 5.1.4.8 Pregnancy Test Analyses

Urine pregnancy test is taken at screening, initial, touch-up, and Month 6. Subjects with positive result will be presented as listing.

### 5.1.5 Subgroup Analyses

Subgroup analyses of the primary effectiveness endpoint will be performed by baseline lip LFS score and volume injected ( $\leq$  median vs  $>$  median). All analyses will be repeated for each investigational site descriptively.

**Table 5-23 Subgroup Analyses**

Endpoint	Description	Timing	Methodology
LFS Responder as assessed by EI by baseline LFS score	Number (%) of responders by treatment group by baseline LFS score	Month 3	Categorical count
LFS Responder as	Number (%) of responders by	Month 3	Categorical count

Endpoint	Description	Timing	Methodology
assessed by EI by volume injected	treatment group by volume injected ( $\leq$ median, and $>$ median)		
All analyses by investigational site	Summary by investigational site	As described in Table 5-15, 5-16, 5-17	As described in Table 5-15, 5-16, 5-17

### 5.1.6 Interim Analyses

Not applicable.

### 5.2 Determination of Sample Size

Up to 176 subjects will be randomized at up to 9 Chinese sites.

**Table 5-24 Sample Size Assumptions**

Parameter	Assumption / Estimate
Primary endpoint	Lip fullness assessment responder
Risk difference 	34.1% (79% Volbella vs 44.1% Control)
SD	NA
$\alpha$	5%
Sides	2
Power	$>$ 96%
N per group	111 in treatment group, 37 in no-treatment control group
Drop-out Rate	15%
N total randomized	176

 Based on interim data from Study JULIDO-002.

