
Approval Date: 29-Jul-2015

[REDACTED]

Long-term safety data will be collected by telephone call at 9 months after the last treatment for the control group and at 9 and 12 months after the last treatment for the treatment group. Throughout the study, the Treating Investigator (or designee) will monitor the subjects for safety.

DIAGNOSIS AND CRITERIA FOR INCLUSION/EXCLUSION: Chinese adults seeking lip enhancement

INCLUSION:

1. male or female, 18 years of age or older
2. has an overall baseline score of Minimal, Mild, or Moderate on the 5-point LFS, as assessed by the Evaluating Investigator, and desires to achieve at least a 1-point improvement in overall LFS score after treatment

[REDACTED]

4. has the ability to follow study instructions and is likely to complete all required visits

[REDACTED]

EXCLUSION:

1. has lip tattoos, piercings, facial hair, or scars that would interfere with visualization of the lips and perioral area for the effectiveness assessments

[REDACTED]

[REDACTED]

[REDACTED]

[REDACTED]

[REDACTED]

[REDACTED]

[REDACTED]

[REDACTED]

10. is on an ongoing regimen of anti-coagulation therapy (eg, warfarin)

[REDACTED]

Approval Date: 29-Jul-2015

[REDACTED]

14. has current cutaneous inflammatory or infectious processes (eg, acne or herpes), an abscess, an unhealed wound, or a cancerous or precancerous lesion in the mouth area (study treatment may be delayed so that subjects with a history of recurrent oral herpes can take prophylactic antiviral/herpes medication for 2 days)

[REDACTED]

TEST PRODUCT, DEVICE VOLUME, AND MODE OF ADMINISTRATION:
VOLBELLA with Lidocaine hyaluronic acid dermal filler will be injected into the lips and, if needed, the philtral columns using a 30 G x 1/2-inch needle. The appropriate injection volume will be determined by the Treating Investigator but is not to exceed a maximum total of 4.0 mL for initial and touch-up treatments combined.

DURATION OF STUDY: treatment period: 1 to 30 days; follow-up period: up to 12 months

RESPONSE MEASURES:
Effectiveness: The primary effectiveness measure is the Evaluating Investigator's assessment of overall lip fullness using the 5-point LFS. The secondary effectiveness measures are the subject's assessment of overall lip fullness using the 5-point LFS, the volume of the overall lips measured from 3D images, and the lip surface area change measured from 3D images. [REDACTED]

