4.2 Duration

The study will span a total of approximately 22 months including an estimated 8 months for recruitment, up to 30 days between screening and randomization, up to 1 month for treatment, and up to 12 months for follow-up. Participation for subjects randomized to the treatment group will encompass up to 1 month for treatment and 12 months of follow-up. Participation for subjects randomized to the no-treatment control group will encompass a 3-month no-treatment period, up to 1 month for optional treatment, and 9 months of follow-up.

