5.1 Number of Subjects

An estimated 176 subjects will be randomized in a 3:1 ratio resulting in 132 subjects assigned to the VOLBELLA with Lidocaine group and 44 subjects assigned to the no-treatment control group. Approximately 148 subjects including 111 treated subjects and 37 untreated control subjects will complete the 3-month visit (primary endpoint) with an anticipated dropout rate of 15% by month 3. An estimated 133 subjects will complete the 12-month visit (end of study) based on an anticipated dropout rate of 10% after month 3.

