8.5 Sample Size Calculation

A sample size of 111 randomized subjects treated with VOLBELLA with Lidocaine and 37 randomized untreated control subjects will provide > 96% power to detect the superiority of VOLBELLA with Lidocaine over no treatment for responder rate at month 3. Responder rate is the percentage of subjects who show at least a 1-point improvement compared with baseline on the 5-point LFS based on the Evaluating Investigator's assessment of overall lip fullness. A 2-sided Fisher's Exact test with 5% significance level will be used to calculate the power, assuming responder rates of 79.0% for the VOLBELLA with Lidocaine group and up to 44.1% for the no-treatment control group at month 3 (based on interim data from Study [JULIDO-002](#)). The power calculation was performed using an Inequality Test for 2 Independent Proportion [Difference] procedure in PASS software (Version 2008). The planned sample size is considered to be adequate for evaluation of long-term (ie, 12-month) safety.

Allowing for attrition of 15% up to month 3 due to early discontinuations, missed visits, or out-of-analysis-window visits, 176 subjects will be randomized, with at least 132 subjects assigned to the VOLBELLA with Lidocaine group and approximately 44 subjects assigned to the no-treatment control group.

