### **4.1 Study Design Summary**

#### **4.1.1 Overall Design**

This is a randomized, multicenter, no-treatment-controlled study of the safety and effectiveness of JUVÉDERM® VOLBELLA® with Lidocaine for lip enhancement in Chinese adults. Subjects will be randomized at a 3:1 ratio either to have treatment with VOLBELLA with Lidocaine at the outset of the study (VOLBELLA with Lidocaine group, also referred to as the treatment group, or VOLBELLA group) or to have treatment delayed by 3 months (no-treatment control group, also referred to as the control group). Subjects with Lip Fullness Scale (LFS) score of Minimal, Mild, or Moderate as assessed by Evaluating Investigator (EI) will be enrolled in the study based on inclusion criteria. Randomization will be stratified by baseline LFS score (ie, LFS score rated as Minimal, Mild, or Moderate at the randomization visit by EI).

Treatment and safety assessments of a subject throughout the study will be performed by the same Treating Investigator(TI) (maximum 2 TIs per site), and effectiveness assessments will be performed by the same EI. The EI will remain blinded to treatment assignments throughout the duration of the study.

For subjects randomized to the treatment group, the study treatment will be on the same day as randomization (or within 30 days after screening). Subjects may undergo an optional touch-up treatment at the day 30 visit after initial treatment, if the TI assesses that optimal correction was not achieved. Routine follow-up visits for safety and effectiveness will occur at 1, 3, and 6 months after the last treatment (initial or touch-up treatment, whichever is last). Long-term safety data will be collected by telephone call at 9 and 12 months after the last treatment.

Meanwhile, subjects randomized to the no-treatment control group will attend study visits at months 1 and 3 of the no-treatment control period. After the completion of the control period, control group will receive optional treatment and optional touch-up treatment. Routine follow-up visits will occur at 1, 3, and 6 months. Safety follow-up phone call will be at 9 months.

At initial treatment visit, the TI will inject the treatment into the vermilion body, vermilion border (including the Cupid's bow), and philtral columns, as needed for lip enhancement. The

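### Do the 34.1-point difference in SAP Table 5-24 and the 133 twelve-month completers in Protocol 5.1 call for a change to the plan?

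*SAP*

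**What the plan says.** **Design difference.** The risk-difference row of SAP Table 5-24 reads "34.1% (79% Volbella vs 44.1% Control"), beside a two-sided 5% level, power above 96%, 111 and 37 subjects per group, 15% dropout and 176 randomized. Protocol 8.5 describes the same calculation by its rates alone, "assuming responder rates of 79.0% for the VOLBELLA with Lidocaine group and up to 44.1% for the no-treatment control group at month 3", using Fisher's exact test. The synopsis repeats those rates. Neither protocol passage prints a difference.

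**Completers.** Protocol 5.1 expects 148 subjects (111 and 37) at Month 3 and then states: "An estimated 133 subjects will complete the 12-month visit (end of study) based on an anticipated dropout rate of 10% after month 3".

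**Length of follow-up.** Protocol 4.2 gives the control arm "a 3-month no-treatment period, up to 1 month for optional treatment, and 9 months of follow-up". The synopsis (Study Design) places the long-term safety telephone calls "at 9 months after the last treatment for the control group and at 9 and 12 months after the last treatment" for the treatment group. SAP 4.1.1 agrees for controls: "Safety follow-up phone call will be at 9 months".

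**Long-term safety.** Protocol 8.5 adds: "The planned sample size is considered to be adequate for evaluation of long-term (ie, 12-month) safety".

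**The concern.** The sample-size table contradicts itself within one cell. A reader who took 34.1 as the real design difference might doubt the stated power, or suspect that one of the two rates is wrong.

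The 133 raises a different doubt. No 12-month visit is described for either arm: the last routine visit is at Month 6, and contact after that is by telephone. Controls have no contact 12 months after last treatment. For a filler, safety exposure is naturally counted from injection. Someone who set the 133 beside the claim in Protocol 8.5 about 12-month safety could therefore believe that 133 people will have been followed for a year after treatment, when only the treatment group can supply such subjects.

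**Working it through.** **1. The difference.** Inputs: 79.0% and 44.1% (Protocol 8.5, synopsis, SAP Table 5-24).

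79.0 - 44.1 = 34.9 points. The table prints 34.1, so the error is 34.9 - 34.1 = 0.8 points. Both rates agree in all three places, so the difference is the outlier and not either rate.

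**2. The stated power.** Inputs: 111 and 37 evaluable subjects, two-sided Fisher's exact test at 5%. Power is the sum, over all pairs of responder counts (x, y) with Fisher p < 0.05, of Bin(x; 111, p1) x Bin(y; 37, p2).

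| Rates | Difference | Exact Fisher power |
|---|---|---|
| 79.0% vs 44.1% (as stated) | 34.9 | 96.7% |
| 79.0% vs 44.9% | 34.1 | 96.1% |
| 78.2% vs 44.1% | 34.1 | 95.9% |

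The first row reproduces the plan's figure of more than 96%. Two approximations at the stated rates agree with it: 97.6% (pooled normal) and 96.3% (continuity-corrected). The power was therefore calculated from the rates, and the misprinted difference did not enter it.

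**3. The number randomized.** 111/0.85 = 130.6, rounded up to 131. 37/0.85 = 43.5, rounded up to 44. The sum is 175. The plan's 132 + 44 = 176 is one more and keeps the 3:1 ratio exactly.

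**4. The 133.** Inputs: 148 at Month 3 and a further 10% loss (Protocol 5.1).

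148 x (1 - 0.10) = 133.2, so the stated figure is reproduced. By arm, assuming the same 10% loss in each (Protocol 5.1 does not say so):

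- treatment group: 111 x 0.90 = 99.9, about 100
- controls: 37 x 0.90 = 33.3, about 33

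These sum to 133.

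**5. What 12 months means in each arm** (Protocol 4.2).

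- Treatment group: up to 1 month of treatment plus 12 months. The study ends 12 months after last treatment, which is 12 to 13 months from first treatment.
- Controls: 3 + (0 to 1) + 9 = 12 to 13 months after randomization, and 9 months after last treatment for those who take the optional treatment.

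The label fits both arms if each has its own time origin: last treatment for the treatment group, randomization for controls. Protocol 8.2.1 and 8.3.1 already use that convention for Month 3. The label fits only the roughly 100 treatment-group subjects if the clock must start at last treatment in both arms.

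**The case for a change.** The best case for acting is that both repairs are cheap and the study supports a pre-market application. A sample-size table should show the difference on which its power rests. One reading of 34.1 (78.2% vs 44.1%) even gives 95.9%, just under the stated power. On the safety side, time since injection is the relevant clock. With no events observed, the one-sided 95% upper bound, 1 - 0.05^(1/n), is 3.0% at n = 100 and 2.2% at n = 133, so a misreading would flatter the precision by about 0.8 points.

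Part of this stands. The subtraction is wrong, and Protocol 5.1 leaves out the time origin and calls a telephone call a visit.

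The rest does not carry far. The 95.9% requires changing a rate that is printed consistently in three places. Protocol 8.5 does not cite 133 in support of its safety statement, and Protocol 5.1 does not mention safety, so the overcount arises only if the reader joins two sections that the documents leave separate. The documents set no precision target for 12-month safety, so adding a bound would be new content and not a correction. Nor is a firm count by arm available. Protocol 8.5 describes its allowance as "Allowing for attrition of 15% up to month 3 due to early discontinuations, missed visits, or out-of-analysis-window visits", so some of those subjects may remain in the study. If all of them did, 176 x 0.90 = 158.4 would finish, which no longer matches the dropout reading in Protocol 5.1. Replacing 133 with finer numbers would require assumptions that the plan does not make.

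**Conclusion.** No change to the plan is needed.

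The 34.1 is a clerical slip of 0.8 points, and the correct value, 34.9, can be read from the two rates in the same cell. Power (96.7% exact, stated as more than 96%), the 111 and 37 evaluable subjects and the 176 randomized all stand. The primary Fisher test uses observed responders and never refers to the design difference.

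The 133 is correct arithmetic for end-of-study completers in both arms, and the text marks it as end of study. What is missing is detail: the time origin, the split by arm, and the fact that the last contact is a call. The synopsis, Protocol 4.2 and SAP 4.1.1 supply the schedule, so an analyst summarizing long-term safety would count time after treatment separately for each arm without further instruction. The split of about 100 and 33 assumes that all the 15% leave by Month 3 and that the later 10% loss is equal in both arms. The number of controls with 9 months after treatment will be lower if some decline the optional treatment.
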